
9.2. Definition of Serious Adverse Event

If an event is not an AE per the definition above, then it cannot be an SAE even if serious conditions are met (eg, hospitalization or death due to disease progression).

A serious adverse event is defined as any untoward medical occurrence that, at any dose:
a. Results in death
b. Is life-threatening The term "life-threatening" in the definition of "serious" refers to an adverse drug experience that places the participant, in the opinion of the initial reporter, at immediate risk of death from the adverse experience as it occurs. This does not include an adverse drug experience that, had it occurred in a more severe form, might have caused death.
c. Requires inpatient hospitalization or prolongation of existing hospitalization In general, hospitalization signifies that the participant has been detained (involving at least an overnight stay) at the hospital or emergency department for observation and/or treatment that would not have been appropriate in the physician's office or outpatient setting. Complications that occur during hospitalization are AEs. If a complication prolongs hospitalization or fulfills any other serious criteria, the event is serious. When in doubt as to whether hospitalization occurred or was necessary, the AE should be considered serious. Hospitalization for elective treatment or planned surgery (eg, stent replacement, hip surgery) is not considered an SAE. Hospitalization for medical interventions in which no unfavorable medical occurrence occurred (ie, elective procedures or routine medical visits) is not considered an SAE.
d. Results in persistent or significant disability/incapacity The term "disability" means a substantial disruption of a person's ability to conduct normal life functions. This definition is not intended to include experiences of relatively minor medical significance, such as uncomplicated headache, nausea, vomiting, diarrhea, influenza, and accidental trauma (eg, sprained ankle), that may interfere with or prevent everyday life functions but do not constitute a substantial disruption.
e. Is a congenital anomaly/birth defect
f. Is an important medical event An important medical event is an event that may not result in death, be immediately life-threatening, or require hospitalization but may be considered serious when, based on appropriate medical judgment, the event may jeopardize the participant and may require medical or surgical intervention to prevent one of the outcomes listed in the above definition. Examples of such events include new invasive or malignant cancers; intensive treatment in an emergency department or at home for allergic bronchospasm, blood dyscrasias, or convulsions that do not result in hospitalization; development of drug dependency or drug abuse; or suspected transmission of an infectious agent via a medicinal product. Secondary malignancies should always be considered SAEs.

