5.2. Exclusion Criteria

Participants are excluded from the study if any of the following criteria apply:

1. Treatment with an anti-IgE biologic (eg, omalizumab) within 8 weeks prior to screening.
2. Clearly defined predominant or sole trigger of chronic urticaria (chronic inducible urticaria) including urticaria factitial (symptomatic demographism), cold-, heat-, solar-, pressure-, delayed pressure-, aquagenic, cholinergic-, or contact-urticaria.
3. Other cutaneous or systemic diseases with symptoms of urticaria or angioedema.
4. Other skin or systemic diseases associated with chronic itching (eg, AD, bullous pemphigoid, dermatitis herpetiformis, senile pruritus, or psoriasis) that, in the investigator's opinion, might influence the study evaluations and results.
5. Women who are pregnant (or who are considering pregnancy) or breastfeeding.
6. Concurrent conditions or history of other diseases, as follows:
 - a. Thrombocytopenia, coagulopathy, or platelet dysfunction.
 - b. Venous and arterial thrombosis, deep vein thrombosis, pulmonary embolism, stroke, moderate to severe heart failure (NYHA Class III or IV), cerebrovascular accident, MI, coronary stenting, or CABG surgery.
 - c. Diagnosis of other significant cardiovascular diseases, including but not limited to angina, peripheral arterial disease, or uncontrolled arrhythmias such as atrial fibrillation, supraventricular tachycardia, ventricular tachycardia, and forms of carditis.
 - d. Uncontrolled hypertension, as defined by a confirmed systolic blood pressure > 160 mm Hg or diastolic blood pressure > 100 mm Hg.
 - e. Participants who are permanently bedridden or wheelchair assisted.
 - f. Recipient of an organ transplant that requires continued immunosuppression.
 - g. Any malignancies or history of malignancies with the exception of adequately treated or excised nonmetastatic basal cell or squamous cell cancer of the skin, or cervical carcinoma in situ.
 - h. Conditions that could interfere with drug absorption, including but not limited to short-bowel syndrome.
 - i. Chronic or recurrent infectious disease, including but not limited to chronic renal infection, chronic chest infection (eg, bronchiectasis), recurrent urinary tract infection (recurrent pyelonephritis or chronic nonremitting cystitis), fungal infection, prior prosthetic joint infection at any time, or open, draining, or infected skin wounds or ulcers.

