6.7.4. Prohibited Medications and Procedures

The following medications and procedures are prohibited for all participants in the study:

- Conventional therapies with potential therapeutic impact on CSU, per discretion of the investigator or designee, with the exception of SOC and rescue medication.
- JAK inhibitors (systemic or topical) other than povorcitinib.
- Use of biologics with immunomodulatory effect.
- Systemic immunosuppressive or immunomodulating drugs (eg, oral or injectable corticosteroids, methotrexate, cyclosporine, dapsone, azathioprine).
- Apremilast, crisaborole, or any other systemic or topical PDE-4 inhibitor.

- Strong systemic CYP3A4 inhibitors and strong and moderate systemic CYP3A4 inducers (see [Appendix B](#)). Examples include but are not limited to the following medications: rifampicin/rifampin, ketoconazole, itraconazole, carbamazepine, ritonavir, St John's wort, and grapefruit/grapefruit juice.
 - In exceptional cases (eg, COVID-19 treatment with nirmatrelvir/ritonavir), and after study drug interruption, strong CYP3A4 inhibitors or strong/moderate inducers may be used for up to 7 days. The sponsor (or designee) must be informed of the investigator's (or designee's) decision and rationale within a reasonable timeframe. Study drug may be restarted after a minimum of 7 days of discontinuation of the strong CYP3A4 inhibitor or strong/moderate inducer.
 - If treatment with strong CYP3A4 inhibitors or strong/moderate CYP3A4 inducers is required for longer than 7 days after study drug interruption, the participant may be discontinued from the study and the ET visit performed.
- Live, attenuated vaccines (during the study and within 8 weeks after the last dose of study drug). Examples of live vaccines include but are not limited to the following:
 - BCG
 - herpes zoster
 - measles-mumps-rubella or measles-mumps-rubella-varicella
 - monovalent, live, attenuated influenza A (intranasal)
 - oral polio vaccine
 - rotavirus
 - seasonal, trivalent, live, attenuated influenza (intranasal)
 - smallpox
 - typhoid
 - varicella (chickenpox)
 - yellow fever
- Elective surgery
 - PC period: Will not be allowed
 - EXT period: May be allowed per determination of the investigator (or designee) after consultation with the sponsor (or designee). See Section [6.6.1.6](#) for details on study drug interruption.

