
• Any safety assessments (eg, ECG, vital signs measurements), including those that worsen from baseline, considered clinically significant in the medical and scientific judgment of the investigator (ie, not related to disease progression) are to be reported as an AE.• Abnormal laboratory test results are to be reported as an AE if they are considered clinically meaningful, induce clinical signs or symptoms, require concomitant therapy, or require changes in study drug. Whenever possible, a diagnosis (eg, anemia, thrombocytopenia) should be recorded in the eCRF rather than the abnormal laboratory test result (eg, low hemoglobin, platelet count decreased).• Exacerbation of a chronic or intermittent pre-existing condition/disease, including either an increase in the frequency and/or intensity of the condition, is to be reported as an AE.• New conditions detected or diagnosed after the start of study drug administration are to be reported as an AE.• New signs and/or symptoms due to the study disease that develop after the first dose of study drug are to be reported as an AE.• Signs, symptoms, or the clinical sequelae of a suspected drug-drug interaction are to be reported as an AE.• Signs and/or symptoms from dose administration errors of a study drug (eg, overdose) or a concomitant medication are to be reported as an AE.• "Lack of efficacy," "disease progression," or "failure of expected pharmacological action" will not be reported as an AE or SAE. Such instances will be captured in the efficacy assessments. However, the signs, symptoms, and/or clinical sequelae resulting from lack of efficacy will be reported as AE or SAE if they fulfil the definition of an AE or SAE. If judged by the investigator more severe than expected for the participant's condition, any clinically significant abnormal laboratory findings or other abnormal safety assessments that are associated with the underlying disease can be reported as an AE or SAE. And if judged by the investigator more severe than expected for the participant's condition, the disease/disorder being studied or its expected progression, signs, or symptoms can be reported as an AE or SAE.• A condition that leads to a medical or surgical procedure (eg, endoscopy, appendectomy) will be reported as an AE if it occurs after obtaining informed consent. If the condition is present before entering the study, then it should be captured as medical history.• Pre-existing diseases, pre-existing conditions, or new conditions with expected fluctuations in signs or symptoms should be reported as an AE only if the investigator judges the fluctuation to have worsened more than expected during study participation.

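### Protocol 9.2 exempts scheduled hospital admissions from SAE status even when the condition arose or worsened after consent

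*Protocol*

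**What the plan says.** Protocol 9.2, criterion c, makes inpatient hospitalization a ground for seriousness and then lists two exemptions. The first is "Hospitalization for elective treatment or planned surgery (eg, stent replacement, hip surgery) is not considered an SAE". The second is "Hospitalization for medical interventions in which no unfavorable medical occurrence occurred (ie, elective procedures or routine medical visits) is not considered an SAE". Only the second carries a condition, namely that nothing untoward occurred.

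The same section has provisions that pull the other way. On complications: "If a complication prolongs hospitalization or fulfills any other serious criteria, the event is serious". On doubtful cases: "When in doubt as to whether hospitalization occurred or was necessary, the AE should be considered serious". Criterion f covers important medical events, where "the event may jeopardize the participant and may require medical or surgical intervention to prevent one of the outcomes" listed in the definition.

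Protocol 9.1 divides conditions that lead to a procedure by consent date. Such a condition "will be reported as an AE if it occurs after obtaining informed consent"; if it was there before study entry it is medical history. Protocol 9.3 draws the same line for recording: what begins or worsens after consent goes on the Adverse Events Form, and what was already present goes on the Medical History Form.

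On timing, Protocol 6.7.4 rules out elective surgery in the placebo-controlled (PC) period and says it may be permitted in the extension (EXT) after the sponsor has been consulted. Every participant in the extension is assigned povorcitinib.

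**The concern.** The consent-date boundary used in 9.1 and 9.3 is missing from 9.2, at the point where seriousness is decided. Take a condition that first appears in the extension and is treated by a scheduled inpatient admission. Section 9.1 makes it an AE. The first exemption in 9.2 then removes hospitalization as a reason to call it serious. If no other criterion applies, it is a non-serious AE.

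Three outputs depend on that label:

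- the 24-hour report to the sponsor (Protocol 9.4);
- the serious-TEAE and treatment-related serious-TEAE summaries (SAP 9.2.2);
- the serious-infection AESI, which Protocol 9.6.1 defines by the SAE criteria and SAP Table 6 finds by searching serious AEs.

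The protocol itself lists infection, thrombosis and malignancy as class risks (Table 4), so consistent classification of serious events matters in this trial.

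**Working it through.** The plan states no figure on this point, so there is none to reproduce. The check has two parts: how the text reads, and how large the effect could be.

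**1. Does other text restore the hospitalization criterion?**

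| Provision | What it covers | Closes the gap? |
|---|---|---|
| Opening of 9.2: a non-AE cannot be an SAE | Makes AE status necessary for SAE status | No. The event is already an AE; the consent rule is not carried into the exemption |
| Second exemption, limited to no untoward occurrence | Its own sentence only | No. If the first sentence carried the same limit, it would add nothing |
| Doubt rule | Whether an admission happened or was needed | No. It does not address whether an elective admission counts |
| Complication rule | Events during the stay | No. It does not reach the condition that caused the stay |
| Important medical event | The condition itself | Sometimes, by investigator judgment |
| Secondary malignancies always SAEs | Malignancies | Yes, for those only |

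The loss is therefore confined to events whose sole seriousness criterion is the scheduled admission.

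**2. Where would such events fall?**

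Inputs: 136 participants, 34 per arm, 12-week PC period, 24-week extension (Protocol Table 2 and 10.1). Planned on-treatment person-weeks:

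- Placebo, PC: 34 × 12 = 408
- Povorcitinib, PC: 102 × 12 = 1,224
- Extension, all povorcitinib: 136 × 24 = 3,264
- Total: 4,896

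Povorcitinib share: (1,224 + 3,264) / 4,896 = 4,488 / 4,896 = 91.7%. If extension time is 30% lower (assumed), extension time is 2,284.8 and the share is 3,508.8 / 3,916.8 = 89.6%.

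For permitted elective surgery on study treatment, eligible time is the extension only, so 100% lies in a povorcitinib period. For other elective treatment, which 6.7.4 does not bar in the PC period, an even spread gives 91.7% on povorcitinib and 408 / 4,896 = 8.3% on placebo.

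**3. How many?**

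The documents give no rate of elective admission. Extension person-years: 3,264 / 52.18 = 62.6.

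| Assumed rate per 100 person-years | Expected elective admissions, whole extension |
|---|---|
| 1 | 0.6 |
| 2 | 1.3 |
| 5 | 3.1 |

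These counts include admissions for pre-existing conditions and events that are serious on other grounds, so the number misclassified would be lower.

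**4. What does one event do to a reported percentage?**

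SAP 5.2 gives the extension six columns: three continuing-dose groups of about 34 and three crossover groups of about 34 / 3 ≈ 11. SAP 9.1 limits the overall safety summaries to participants who received only povorcitinib, again about 34 per dose.

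- 1 / 34 = 2.9 points
- 1 / 11 = 9.1 points

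**The case against.** The strongest reply is that a sensible investigator would not read the exemption this way. The second exemption describes elective procedures as ones without an untoward occurrence, and both examples (a replacement stent, a hip operation) fit long-standing conditions. That reading is reasonable, and many sites would adopt it. It is not what the first sentence says, and seriousness should not vary with which of two adjacent sentences a site follows.

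It is also fair that the events are not hidden. The condition stays an AE. Elective surgery in the extension requires consultation with the sponsor. Study drug is interrupted at least a week beforehand, and TEAEs leading to interruption are tabulated. For events that CTCAE does not classify, an indicated hospitalization is Grade 3, and Grade 3 or higher TEAEs are tabulated. All of this stands. What is lost is the serious label and what follows from it.

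The infection case is narrow: it needs a new infection admitted as scheduled treatment. Opportunistic infections, herpes zoster and TB are AESIs whether serious or not.

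Several stronger readings are tempting, and the documents do not support them:

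- A reader might infer that the surgery rule is what places the lost SAEs on povorcitinib. Planned on-treatment time is already 91.7% povorcitinib; the rule only moves the surgical part from there to 100%.
- A reader might infer bias against placebo in the randomized comparison. The exemption applies to all arms alike, elective surgery is barred in those 12 weeks, and the extension has no placebo group. Protocol 10.4 plans the final analysis without statistical comparison to placebo.
- A reader might take the stent example, set beside the exclusion of prior "cerebrovascular accident, MI, coronary stenting, or CABG surgery", as proof that a first coronary stent on study is listed as exempt. The example is a replacement, and it does not say coronary.
- A reader might pool continuing and crossover participants to about 34 + 11.3 = 45.3 per dose, or 2.2 points per event. No planned safety column has that denominator.

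**Conclusion.** The wording gap is real. As written, 9.2 removes the hospitalization criterion from any scheduled admission, including one for a condition that began or worsened after consent, and the other provisions restore it only in part and mostly by judgment.

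The effect is probably small: well under one to about three elective admissions in the whole extension at the assumed rates, of which only some would be misclassified. It bears mainly on the extension and povorcitinib-only overall serious-TEAE counts, where columns of 34 and 11 make a single event visible, and on prompt reporting of the individual case. The randomized 12-week safety comparison is not materially affected. These sizes rest on planned enrolment, full planned exposure, an equal split of crossovers and assumed admission rates; the reading of the text rests on none of them.

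**What to change.** In 9.2, criterion c, restrict the first exemption to an admission that was planned before the ICF was signed, for a condition present at that time that has not worsened on study. Add that an inpatient admission, scheduled or not, for a condition that began or worsened after consent meets criterion c. Align the eCRF guidelines so that sites record whether the admission was planned before consent.

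The cost is a short protocol edit, an update to the guidelines and a few more SAE reports. No analysis in the SAP needs to change, because its serious-TEAE and serious-infection outputs use the classification they receive.

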9.3. Recording and Follow-Up of Adverse Events and/or Serious Adverse Events

Adverse Event and Serious Adverse Event Recording

- An AE/SAE that begins or worsens after informed consent is signed should be recorded on the Adverse Events Form in the eCRF. All AEs/SAEs should be reported for randomized participants, but only SAEs need to be reported for screen failure participants. For randomized participants, conditions that were present at the time informed consent was given should be recorded on the Medical History Form in the eCRF. For detailed information, refer to the eCRF guidelines.
- When an AE/SAE occurs, it is the responsibility of the investigator to review all documentation (eg, hospital progress notes, laboratory reports, and diagnostic reports) related to the event.
- The investigator (or designee) will then record all relevant AE/SAE information in the eCRF.
- It is **not** acceptable for the investigator to send photocopies of the participant's medical records in lieu of completing the Adverse Events Form in the eCRF.
- There may be rare instances when copies of medical records for certain cases are requested. In this case, all participant identifiers, with the exception of the participant number, will be redacted by the site staff on the copies of the medical records before submission. These records can be submitted to Incyte Pharmacovigilance by email/fax per the contact information listed in the Study Binder as per SAE completing guidelines.
- The investigator will attempt to establish a diagnosis of the event based on signs, symptoms, and/or other clinical information. Whenever possible, the diagnosis (not the individual signs/symptoms) will be documented as the AE/SAE. When a clear diagnosis cannot be identified, each sign or symptom should be reported as a separate AE/SAE.

To the extent possible, each AE/SAE should be evaluated to determine the following:

- The severity grade (CTCAE v5.0 Grade 1 to 5). See below for further instructions on the assessment of intensity.
- Whether there is at least a reasonable possibility that the AE is related to the study drug: suspected (yes) or not suspected (no). See below for further instructions on the assessment of causality.
- The start and end dates, unless unresolved at the final post-treatment follow-up visit.
- The action taken with regard to study drug as a result of the AE/SAE(s).
- The event outcome (eg, not recovered/not resolved, recovered/resolved, recovering/resolving, recovered/resolved with sequelae, fatal, unknown).
- The seriousness, as per the SAE definition provided in Section 9.2.
- The action taken with regard to the event. Note: If an AE is treated with a concomitant medication or non-drug therapy, this action should be recorded on the Adverse Events Form and the treatment should be specified on the appropriate eCRF (eg, Prior/Concomitant Medications, Procedures and Non-Drug Therapy).

Assessment of Intensity

The severity of AEs will be assessed using CTCAE v5.0 Grades 1 through 5. If an event is not classified by CTCAE, the severity of the AE will be graded according to the scale below to estimate the grade of severity.

The investigator will make an assessment of intensity for each AE and SAE reported during the study and assign it to 1 of the following categories:

- **Grade 1:** Mild; asymptomatic or mild symptoms; clinical or diagnostic observations only; treatment not indicated.
- **Grade 2:** Moderate; minimal, local, or noninvasive treatment indicated; limiting age-appropriate activities of daily living.
- **Grade 3:** Severe or medically significant but not immediately life-threatening; hospitalization or prolongation of hospitalization indicated; disabling; limiting self-care activities of daily living.
- **Grade 4:** Life-threatening consequences; urgent treatment indicated.
- **Grade 5:** Fatal.

Assessment of Causality

- The investigator is obligated to assess the relationship between study drug and each occurrence of each AE/SAE.
- A "reasonable possibility" of a relationship conveys that there are medical facts, evidence, and/or arguments to suggest a causal relationship, rather than that a relationship cannot be ruled out.
- The investigator will use clinical judgment to determine the possibility of a relationship.
- The investigator will also consult the RSI in the IB in making their assessment.
- Alternative causes, such as underlying or concurrent disease(s), concomitant therapy, and other risk factors, as well as the temporal relationship of the event to study drug administration, will be considered and investigated.
- For each AE/SAE, the investigator **must** document in the medical notes that they have reviewed the AE/SAE and have provided an assessment of causality.
- With regard to assessing causality of SAEs:
 - There may be situations in which an SAE has occurred and the investigator has minimal information to include in the initial report. However, the causality assessment is one of the criteria used when determining regulatory reporting requirements. **Therefore, it is very important that the investigator always make an assessment of causality based on the available information for every event before the initial transmission of the SAE.**
 - The investigator may change their opinion of causality in light of follow-up information and submit the updated causality assessment.

Follow-Up of Adverse Events and Serious Adverse Events

- The investigator is obligated to perform or arrange for the conduct of supplemental measurements and/or evaluations as medically indicated or as requested by the sponsor to elucidate the nature and/or causality of the AE or SAE as fully as possible. This may include additional laboratory tests or investigations, histopathological examinations, or consultation with other health care professionals.
- Once an AE is detected, it should be followed in the Adverse Events Form in the eCRF until it has resolved or until it is judged to be permanent; assessment should be made at each visit (or more frequently if necessary) of any changes in severity, the suspected relationship to the study drug, the interventions required to treat the event, and the outcome.
- When the severity of an AE changes over time for a reporting period (eg, between visits), each change in severity will be reported as a separate AE.
- If a participant dies during participation in the study or during a recognized follow-up period, the investigator will provide the sponsor with a copy of any postmortem findings, including histopathology.
- Updated SAE information will be recorded in the originally completed eCRF and reported to Incyte Pharmacovigilance (in the SAE EDC CRF) until resolution, stabilization, the event is otherwise explained, or the participant is lost to follow-up.
- Any updated SAE data (including SAEs being downgraded to nonserious) will be submitted to the sponsor (or designee) within 24 hours of receipt of the information.

